Methocarbamol and Orphenadrine for Acute, Non-traumatic, Non-radicular Low Back Pain: A Randomized, Placebo Controlled, 3-armed Study

NCT#: NCT02665286 Protocol ID: 2015-5903 Version Date: 01/27/2016

[name] Professor and Vice-Chair for Clinical Investigations Department of Emergency Medicine Montefiore Medical Center Albert Einstein College of Medicine

Specific Aims

Low back pain (LBP) causes 2.4% of visits to US emergency departments (ED) resulting in 2.7 million visits annually. (1) In general, outcomes for these patients are unfavorable. One week after ED discharge, 70% of patients report persistent back-pain related functional impairment and 69% report analgesic use within the previous 24 hours.(2) Three months after the emergency visit, 48% of ED LBP patients report functional impairment, 42% report moderate or severe pain, and 46% report persistent analgesic use. (2)

It is not clear which medications should be prescribed for acute LBP. Non-steroidal anti-inflammatory drugs (NSAID) are more efficacious than placebo with regard to LBP relief, global improvement, and requirement of analgesic medication (3) but are insufficient treatment for as many as ½ of ED patients, who continue to suffer despite use of NSAIDs. Treatment of LBP with multiple concurrent medications is common in the ED--emergency physicians often prescribe skeletal muscle relaxants or opioids in combination with NSAIDs.(4) However, work recently completed has revealed that combining cyclobenzaprine, a skeletal muscle relaxant, or oxycodone/acetaminophen with an NSAID does not improve outcomes.(5) It remains uncertain if adding other skeletal muscle relaxants to NSAIDs improves LBP outcomes.

Two specific skeletal muscle relaxants, orphenadrine and methocarbamol, are each used in more than 250,000 U.S. ED visits for LBP annually, although scant evidence exists to determine the appropriateness of this approach.(6) Orphenadrine is centrally acting with prominent anti-cholinergic and anti-histaminic properties. Mechanism of action is not understood. Efficacy in low back pain may be related to non-specific analgesic properties. Mechanism of action of methocarbamol has also not been established. Its efficacy is thought to be related to CNS effects rather than direct effects on skeletal muscles.

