- Absence of non-musculoskeletal etiology of low back, such as urinary tract infection, ovarian cysts, or influenza like illness. The primary clinical diagnosis, at the conclusion of the ED visit, must be a diagnosis consistent with non-traumatic, non-radicular, musculoskeletal LBP.

-Patient is to be discharged home. Patients admitted to the hospital are more likely to be treated with parenteral medication and therefore are not appropriate for this study.

- Age 18-69 Enrollment will be limited to adults younger than 70 years because of the increased risk of adverse medication effects in the elderly.

-Non-radicular pain: pain cannot radiate below the gluteal folds in a radicular pattern. Patients with non-radicular pain extending below the gluteal folds will not be excluded

-Pain duration ≤ 2 weeks (336 hours). Patients with more than two weeks of pain are at increased risk of poor pain and functional outcomes.(2)

-Prior to the acute attack of LBP, back pain cannot have occurred once per month or more frequently. Patients with more frequent back pain are at increased risk of poor pain and functional outcomes.(2)

-Non-traumatic LBP: no substantial and direct trauma to the back within the previous month -Functionally impairing back pain: A baseline score of > 5 on the Roland-Morris Disability Questionnaire (Appendix)

Exclusion criteria:

-Not available for follow-up

-Pregnant or breast-feeding

-Chronic pain syndrome defined as use of any analgesic medication on a daily or near-daily basis -Allergic to or intolerant of investigational medications

-Contra-indications to non-steroidal anti-inflammatory drugs: 1) history of hypersensitivity to NSAIDs or aspirin or patients in whom NSAIDS or aspirin have induced allergic manifestations such as asthma, nasal polyps, rhinitis, or urticarial 2) active or history of peptic ulcer disease, chronic dyspepsia, or active or history of gastrointestinal bleed 3) Severe heart failure (NYHA 2 or worse) 4) hypertension (JNC7 stage 2 or worse) 5) Chronic kidney disease 3 or worse 6) Current use of anti-coagulants, bleeding with tooth brushing, easy bruisability 7) Hepatitis 8) Alcoholism

Naproxen plus orphenadrine or methocarbamol for LBP. An RCT. Version 012716

-Contra-indications to orphenadrine: 1) Glaucoma, Prostatic hypertrophy, Myasthenia gravis, Pyloric or duodenal obstruction

-Contra-indications to methocarbamol: 1) Myasthenia gravis, Chronic kidney disease 3 or worse

Study arms:

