4. Low back pain frequency: "Over the last 24 hours, how often were you in pain? Not at all, Rarely, Sometimes, Usually, Always". Low back pain symptomatology is quite variable. Some patients may experience no pain unless they move a certain way. Others may experience a constant low level of pain. This question will help determine the burdensomeness of the LBP in the patient's daily life.5. Satisfaction, as measured by response to this question: The next time you go to the ER with low back pain, do you want to get the same combination of medications?

Baseline measures

1. Roland Morris LBP disability questionnaire

2. Patient Health Questionnaire depression module, the PHQ 9, will be assessed at the baseline visit.

3. 5-item Cassandra questionnaire. These five questions, based on psychological variables, predict poor outcomes in an emergency room population.(12) (Reproduced in the Appendix)

4. Perceived risk of not recovering. Pain outcomes may be influenced by expectations. After providing an educational intervention, we will ask study participants to estimate how long they believe they will continue to suffer from pain.

Naproxen plus orphenadrine or methocarbamol for LBP. An RCT. Version 012716

5. StarT Back LBP questionnaire

Primary outcome

The change in Roland Morris scale between the baseline ED visit and the one week follow-up (Roland-Morris _{baseline} - Roland-Morris _{1week}). The baseline questions will refer to the time period immediately prior to ED presentation (Before you came to the ER today, were you able to....)..

Secondary outcomes

- The following outcomes will be assessed one week after ED discharge
- 1. Day post ED discharge able to return to all usual activities
- 2. Satisfaction with treatment
- 3. Number of visits to any healthcare provider.

4. Worst LBP over the previous 24 hours, using a four point ordinal scale: severe, moderate, mild, or none and a 0 - 10 verbal integer scale

5. Use of any analgesic or LBP medication within the previous 24 hours.

6. Frequency of low back pain using the five point Likert scale: Not at all, Rarely, Sometimes, Usually, Always

7.Absolute RMDQ score

The following outcomes will be assessed three months after ED discharge

1. Roland Morris Disability Questionnaire

2. Worst LBP over the previous week, using a four point ordinal scale: severe, moderate, mild, or none and a 0 - 10 verbal integer scale

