Prior to discharge from the ED and after the patient's pain has been controlled, the attending emergency physician will refer appropriate patients to study personnel for screening. Eligible patients would have already received different and various medications in the ED for their pain (potentially including naproxen) prior to being approached for study participation. This decision is up to the attending physician and is not related to participation in the study. Patients will be screened and consented. Research associates will ascertain baseline socio-demographic information, low back pain history, and baseline variables discussed above. A urine pregnancy test will be performed. Research personnel will provide each patient with a 15-minute educational intervention. This will be based on NIAMS's Handout on Health: Back Pain information webpage (available at http://www.niams.nih.gov/Health Info/Back Pain/default.asp) Research personnel will review each section of the information sheet with the patient and elicit questions. Patients will be discharged with two medical vials, one containing naproxen and one containing placebo, orphenadrine, or methocarbamol. Patients will be cautioned not to take off protocol LBP medications without first consulting with a healthcare provider. Patients will be cautioned not to drink alcohol or use other centrally-acting substances while using study medications. Patients will be cautioned not to drive after taking the study medications. Follow-up phone calls will be conducted one week and three months after ED discharge. Follow-up will be attempted daily until successful. For patients difficult to contact, express courier or home visit will be used to obtain follow-up information. Analysis. An intention-to-treat analysis will be performed. The primary outcome will be a comparison of the change in RMDQ between baseline and one week. Results will be reported as means with 95%CI. A t-test for independent samples will be used to determine statistically significant differences

between placebo and each of the active medications. Secondary outcomes will be reported as rates with 95%CI. A per protocol efficacy analysis will be conducted among those patients who use the investigational medication at least once.

Sample size calculation

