We based assumptions on a recently completed RCT of LBP treatment. The mean improvement in RMDQ among those who receive naproxen alone was 10.2. The standard deviation was 8.9. A widely accepted minimum clinically important improvement of 5 points on the RMDQ would require those randomized to active medication to demonstrate a mean improvement of 15.2 on the RMDQ. Using a standard alpha of 0.05 and a beta of 0.20, we determined the need for 50 subjects in each arm. To account for protocol violations and patients lost-to-follow-up (typical lost-to-follow-up rate is 5%) and to ensure sufficient power for the per protocol analysis (in our previous ED-based LBP studies, up to 1/3 of enrolled patients have not used the medication more than once), we intend to enroll 80 patients in each arm.

Data Safety Monitoring Committee. This committee will be headed by [name] and include XXX. The committee will meet every month with the PI to 1) monitor adverse events and develop strategies to minimize these; and, 2) monitor recruitment and enrollment. There will not be an interim analysis. Naproxen plus orphenadrine or methocarbamol for LBP. An RCT. Version 012716 6

Registration. The study will be registered at http://www.clinicaltrials.gov.

Consent. Study personnel will obtain informed consent once the patient's pain has been controlled and the patient is ready for discharge from the ED.

Risks/Benefits

Non-steroidals are used in 50% of more than 2.5 million annual US ED visits for LBP. Skeletal muscle relaxants are used in 43% of these visits. Regardless of results, this study will have a national impact. Study subjects will benefit by receiving a medication that is likely to improve their acute LBP. In addition to breach of confidentiality, which is unlikely, and inconvenience to the subject, which will undoubtedly occur, it is likely that subjects will experience adverse medication effects. For the most part, these are nuisance events. Skeletal muscle relaxants such as orphenadrine and methocarbamol are generally well tolerated but can cause substantial drowsiness and when combined with alcohol or other centrally acting substances may be lethal. Non-steroidals can cause life-threating gastro-intestinal bleeding, but this is unlikely in patients screened for gastro-intestinal illness who will take the medication for one week only.

Data Storage & Confidentiality

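### The plan reports every secondary outcome as a rate, but the RMDQ and 0-10 pain outcomes are scores, and no cut-point is named for turning them into rates

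*Combined protocol and SAP*

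**What the plan says.** The analysis paragraph under Details of protocol treats the two classes of outcome differently. For the primary outcome, the change in RMDQ from baseline to one week, it says "Results will be reported as means with 95%CI" and specifies an independent-samples t-test. For everything else it says "Secondary outcomes will be reported as rates with 95%CI". It gives no exception, cut-point or other secondary summary.

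The Secondary outcomes section contains these scores:
- One week, item 7: "Absolute RMDQ score".
- Three months, item 1, under "The following outcomes will be assessed three months after ED discharge": the RMDQ.
- One week item 4 and three months item 2: worst pain on four ordered categories, "or none and a 0 - 10 verbal integer scale".

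The list also includes the day of return to usual activities, the number of days with low back pain, and visits to healthcare providers.

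Three other places bear on a possible RMDQ cut. Inclusion criteria: "Functionally impairing back pain: A baseline score of > 5 on the Roland-Morris Disability Questionnaire". Sample size calculation: "A widely accepted minimum clinically important improvement of 5 points on the RMDQ". Specific Aims, on three-month outcomes: "48% of ED LBP patients report functional impairment", with no threshold given.

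**The concern.** The RMDQ has 24 yes/no items and the pain scale runs from 0 to 10. Neither becomes a rate until someone chooses a threshold. Two analysts who both follow the plan could choose different thresholds and report different three-month results from the same data.

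Two things are at stake. Cutting a score usually widens the confidence interval relative to the effect. And a cut that is not named beforehand can be chosen, even without intent, because it gives the more striking result. Every three-month outcome is secondary, so the RMDQ result at that time rests entirely on this one sentence.

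**Working it through.** **1. Which cuts the documents supply.** For an RMDQ score there is one number, > 5, and it is an entry rule. The 5 points in Sample size calculation is used as a difference between arm means (10.2 + 5 = 15.2), not as a threshold for classifying a patient. Specific Aims gives no threshold. For the 0-10 scale there is no cut at all. None of these is tied to a secondary outcome.

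**2. The plan's own figure.** Inputs from Sample size calculation: difference 5, SD 8.9, alpha 0.05 (taken as two-sided), power 0.80.
n per arm = 2 × (1.960 + 0.842)² × 8.9² / 5² = 49.7, so 50. This agrees with the plan.

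**3. Mean against a cut (illustration).** Evaluable n = 80 × 0.95 = 76 per arm, using the plan's 80 enrolled and 5% loss. The difference of 5 and SD of 8.9 are borrowed from the one-week change score; the documents give no values for three-month RMDQ or for pain. Scores are assumed normal.
- As a mean: half-width = 1.976 × 8.9 × √(2/76) = 2.85 points. Relative to the effect: 2.85 / 5 = 57%.
- Cut midway between the arm means: proportions Φ(−2.5/8.9) = 38.9% and Φ(+2.5/8.9) = 61.1%, a difference of 22.1 percentage points. SE = √[(0.389 × 0.611 + 0.611 × 0.389) / 76] = 7.91 points; half-width = 1.96 × 7.91 = 15.5 points. Relative to the effect: 15.5 / 22.1 = 70%.
- Patients needed for equal relative precision: (0.701 / 0.571)² = 1.51 times.
- Power, if tested at two-sided 0.05: 93% for the mean and 78% for the midpoint cut.

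**4. Scores bounded to the scale.** In 20,000 simulated trials, normal scores with means 8 and 3 and SD 8.9 were rounded and clipped to 0-24. Clipping shrinks the true difference to about 3.5 points (means about 8.8 and 5.2; SDs about 7.2 and 6.1), so this is not the 5-point case.

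| Summary | Power, if tested at two-sided 0.05 |
|---|---|
| Mean | about 90% |
| Cut > 0 | 73% |
| Cut > 5 | 77% |
| Cut > 10 | 73% |

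**5. Choosing between cuts.** With no true difference, the same bounding and common means of 0, 3, 5, 8 or 10, a single cut at > 5 rejects in about 5% of trials. Keeping the better of > 5 and > 0 rejects in about 8-9%. The > 0 cut is an assumption, and the plan states no tests for secondary outcomes.

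**6. A case that goes the other way.** Suppose a drug affected only full recovery: 48% against 30% with any impairment, with scores among the impaired drawn from a normal distribution (mean 10, SD 6) clipped to 1-24 in both arms. The 48% borrows the Specific Aims figure and takes it to mean any impairment; the rest is assumed. Power is 46% for the mean and 64% for a cut at > 0 named in advance.

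**The case against.** The strongest reply is that a mean is not always the better summary. Step 6 shows this: if the benefit is complete recovery in some patients, a cut at zero fixed in advance does better. That stands, and it makes naming the summary beforehand the firmest part of the point. It does not rescue the present sentence, which names no cut.

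A second reply is that the illustration borrows a one-week effect and SD, whereas three-month RMDQ is the most exposed outcome. Study drug is supplied for seven days, and nothing in the documents supports a 5-point difference at three months. That also stands: the figures show the kind of loss to expect and do not forecast it. Power and false-positive figures further presuppose tests that the plan specifies only for the primary outcome.

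Third, some outcomes are less exposed than the list suggests. The change in one-week RMDQ is analysed as a mean. Pain is also recorded in four categories, whose proportions are rates without any cut. Rates suit the yes/no items.

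A reader might infer that the documents contain several competing RMDQ cut-points. They do not: > 5 is the only numeric cut on a score, and it serves another purpose. One might also read the word rates as loose shorthand that includes means. The same paragraph uses both terms and assigns means to the primary outcome, so the text does not support that reading.

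**Conclusion.** The concern holds as a correction to the secondary analyses and should be acted on. Taken literally, the plan turns RMDQ and 0-10 pain into rates at unnamed thresholds. Three-month RMDQ has no other protection.

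Under the stated assumptions the relative half-width rises from 57% to 70% of the effect. In the bounded case, with a difference of about 3.5 points, power falls from about 90% to 73-77%. Choosing the better of two cuts would raise false positives to about 8-9%, if tests were made and if > 0 were the second cut.

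The documents do not support a conclusion that the primary result or the sample size is compromised, that any cut has been or will be picked from the data, or that a rate is always the weaker summary.

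**What to change.** Amend the secondary-outcome sentence in the analysis paragraph as follows:
- Report RMDQ at one week and three months, and 0-10 worst pain at both times, as between-arm mean differences with 95% CI.
- Keep rates with 95% CI for the yes/no and categorical items.
- If a rate is also reported for RMDQ or 0-10 pain, name its cut-point before the data are seen. This also covers an effect on full recovery.
- State one summary in advance for each of day of return to usual activities, number of days with low back pain, and number of visits.

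The cost is a few lines of text and slightly more analysis work. No new data item is needed, and the primary outcome, sample size and follow-up do not change.

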Given the poor pain and functional outcomes that persist beyond an ED visit for acute LBP, we propose a clinical trial to determine whether combining either orphenadrine or methocarbamol with an NSAID is more effective than NSAID monotherapy for the treatment of acute, non-traumatic, non-radicular low back pain. Specifically, we will evaluate the following two hypotheses:

- 1) A daily regimen of naproxen + orphenadrine will provide greater relief of LBP than naproxen + placebo one week after an ED visit, as measured by the Roland Morris Disability Questionnaire
- A daily regimen of naproxen + methocarbamol will provide greater relief of LBP than naproxen + placebo one week after an ED visit, as measured by the Roland Morris Disability Questionnaire

Overview.

This will be a single center, double-blind, comparative effectiveness study, in which we enroll patients during an ED visit for musculoskeletal LBP and follow them by telephone seven days and three months later. Every patient will receive standard-of-care therapy, consisting of naproxen and a low back pain education session. Patients will be randomized to orphenadrine, methocarbamol, or placebo.

Subject selection:

Our goal is to include in this study a broad representation of patients with musculoskeletal back pain who are likely to respond to the investigational medications and who would not be considered candidates for spinal surgery or targeted epidural intervention. We hope for a widely generalizable study and therefore will not require diagnoses to be contingent on advanced imaging studies. Though we could ensure a more homogeneous study population by requiring imaging, we do not believe this is clinically useful and it will not facilitate dissemination and utilization of the study results. The presence or absence of palpable spasm of the paraspinal muscles will be recorded but not used as an entry criterion because the clinical significance and reliability of this finding is uncertain.(7)

Inclusion criteria:

-Present to ED primary for management of LBP, defined as pain originating between the lower border of the scapulae and the upper gluteal folds. Flank pain, that is pain originating from tissues lateral to the paraspinal muscles, will not be included.

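### Should the two drug-versus-placebo primary tests share a single 5% error rate?

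*Combined protocol and SAP*

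**What the plan says.** Specific Aims announces the pair: "Specifically, we will evaluate the following two hypotheses". The first reads "A daily regimen of naproxen + orphenadrine will provide greater relief of LBP than naproxen + placebo one week after an ED visit". The second repeats it with methocarbamol in place of orphenadrine. Both use the Roland Morris questionnaire (RMDQ) at one week, and neither is ranked ahead of the other.

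The Analysis paragraph gives one method for both: "A t-test for independent samples will be used to determine statistically significant differences" "between placebo and each of the active medications". It adds: "Results will be reported as means with 95%CI".

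Sample size calculation takes its inputs from an earlier trial: "The mean improvement in RMDQ among those who receive naproxen alone was 10.2" and "The standard deviation was 8.9". With a target difference of 5 points it concludes: "Using a standard alpha of 0.05 and a beta of 0.20, we determined the need for 50 subjects in each arm". Enrolment is then raised to 80 per arm, to cover losses (5% is called typical) and to keep power for the per-protocol analysis. No interim analysis is planned.

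Study arms and Randomization and blinding describe one control arm. It has two placebo schedules, one of each per block of six, against two assignments to each active drug. Allocation is therefore 1:1:1.

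No Bonferroni, Holm, Dunnett, fixed-sequence or global-test procedure appears, and no reason is given for leaving one out.

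**The concern.** Two unranked primary tests, each given the full 0.05, offer two chances of a false positive. Specific Aims also contains umbrella wording: it asks whether other muscle relaxants add anything to an NSAID, and whether either of these two does. Read that way, success with either drug answers the question, and the error rate that matters is the one across both tests. That rate is above 0.05.

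The shared placebo arm appears to make things worse. If the placebo group does badly by chance, both drugs look good together, and two results that seem to support each other may rest on one accident. The stated 50 per arm also carries no allowance for a second comparison.

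If this were a defect, the trial could report a benefit for a commonly used drug on weaker evidence than its stated alpha suggests. A pre-specified Holm or Dunnett procedure would seem to cure that with one sentence.

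**Working it through.** **Inputs.** From Sample size calculation: difference 5, SD 8.9, alpha 0.05, power 0.80, 80 enrolled per arm, 5% lost, and up to one third not using the medication more than once. From Randomization and blinding: equal arms with the placebo schedules pooled. Sidedness is not stated.

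**The plan's own figure.** n per arm = 2 × SD² × (z for alpha + z for power)² / difference².

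- Two-sided 0.05: 2 × 79.21 × (1.960 + 0.842)² / 25 = 49.7, so 50. This matches the plan (the noncentral t gives 51).
- One-sided 0.05: 2 × 79.21 × (1.645 + 0.842)² / 25 = 39.2, so 40. No match.
- Two-sided 0.025: 2 × 79.21 × (2.241 + 0.842)² / 25 = 60.2, so 61 (noncentral t: 62). No match.

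So alpha was not split, and two-sided testing is the sensible inference. The 95% intervals agree with it.

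**Error rates when neither drug works.** Each contrast has variance 2 × SD²/n. The two contrasts share the placebo mean, so their covariance is SD²/n and their correlation is 0.5. Using a bivariate normal with cut-off 1.96:

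| Event | One test | Two tests, shared control | Two tests, independent |
|---|---|---|---|
| At least one significant, either direction | 5% | 9.07% | 1 − 0.95² = 9.75% |
| At least one false claim of benefit | 2.5% | 4.54% | 1 − 0.975² = 4.94% |
| Both significant, either direction | – | 5 + 5 − 9.07 = 0.93% | 0.05² = 0.25% |

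Simulated t-tests (200,000 trials at each size) give 9.09% at 50 per arm and 9.07% at 80.

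Two things follow. The 9% counts trials in which a drug looks worse than placebo, and such a result would not be a claim for the drug. And sharing a control lowers the chance of at least one error (9.07% against 9.75%). What it raises is the chance of both errors together. Holm and Dunnett control the chance of at least one error; they do not remove the dependence created by an unlucky placebo group.

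**What adjustment would cost.** Power per comparison, noncentral t, difference 5 and SD 8.9:

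| Evaluable per arm | Unadjusted 0.05 | Bonferroni 0.025 | Dunnett, about 0.027 |
|---|---|---|---|
| 76 (80 × 0.95), intention to treat | 93.1% | 88.3% | 88.9% |
| 50.7 (76 × 2/3), worst-case per protocol | 80.0% | 70.9% | 71.9% |

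Holm at 76 per arm, by simulation, gives about 88.5% if one drug works and 91.8% if both do.

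The 50.7 is a pessimistic bound. The one-third is an upper limit and counts patients who used the drug no more than once, whereas the Analysis paragraph keeps in the per-protocol set anyone who used it at least once.

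**The case for a change.** The strongest case for adjusting is this. The trial asks about adding a muscle relaxant to naproxen, expects a national impact, and would be read as positive if either drug succeeded. For the intention-to-treat analysis, Holm costs only about 1 to 5 points of power and no patients. It has to be fixed before unblinding, because an adjustment chosen afterwards carries little weight. Anyone who prefers no adjustment should at least say so in advance.

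Part of this stands. The umbrella wording is there, the relative inflation is real (about 1.8-fold on either count), and intention-to-treat power would stay well above 80%.

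The rest is weaker. The hypotheses as written are specific to each drug, and no rule for an overall win is stated. The cost is small only for intention to treat: 80 per arm was chosen partly to protect the per-protocol analysis, and adjusting that too could take it below 80%. A sentence declaring that no adjustment is intended would record a policy without altering any test. The number of primary comparisons is already fixed by the two hypotheses and the named test, so a reader who wants a stricter threshold can apply 0.025 to each result.

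**Conclusion.** No change is needed. The plan makes a fair trade-off: it controls error at 5% for each of two separate drug questions and accepts 9.1% across both (4.5% for at least one false claim of benefit, against 2.5% for one test). In return it keeps 93.1% power per comparison by intention to treat, and about 80% per protocol in the worst case. A sponsor who chose Holm for the two intention-to-treat tests would also be on firm ground, at about 88.5% to 91.8% power. Reasonable statisticians differ on distinct drugs sharing a control, and the documents make no commitment that the present choice breaks.

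This rests on two-sided tests (inferred from the reproduced 50 per arm and the 95% intervals), equal arms with placebo pooled, the plan's SD of 8.9 and difference of 5, and 5% loss. It also rests on reading the two hypotheses as separate questions. Had the plan promised a 5% rate across both, or called the trial positive if either drug won, the conclusion would be different.

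### The protocol warns of a potentially lethal interaction with centrally acting drugs, but no entry criterion or baseline item identifies patients on a regular non-analgesic sedative

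*Combined protocol and SAP*

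**What the plan says.** Risks/Benefits describes the relaxants as generally well tolerated but able to cause marked drowsiness, and adds that they "when combined with alcohol or other centrally acting substances may be lethal".

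Details of protocol responds with advice to the patient: "Patients will be cautioned not to drink alcohol or use other centrally-acting substances while using study medications". Two neighbouring cautions are "Patients will be cautioned not to take off protocol LBP medications without first consulting with a healthcare provider" and "Patients will be cautioned not to drive after taking the study medications".

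Exclusion criteria touches central nervous system depressants in two places. One is alcoholism, listed among the NSAID contra-indications. The other is "Chronic pain syndrome defined as use of any analgesic medication on a daily or near-daily basis". The drug-specific lists name four conditions for orphenadrine and two for methocarbamol, and no concomitant drug for either. Anti-coagulants are the only other concomitant drug class named.

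Patients reach screening when "the attending emergency physician will refer appropriate patients to study personnel for screening". After that, "Research associates will ascertain baseline socio-demographic information, low back pain history, and baseline variables discussed above". Baseline measures lists five items: the Roland-Morris questionnaire, the PHQ-9, the Cassandra questions, expected recovery and StarT Back. None is a medication history.

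**The concern.** The protocol names a serious interaction and then leaves it to the patient to avoid. A caution works for someone who can choose not to drink, or not to take an occasional tablet, for a week. It does not work well for someone on a nightly hypnotic or a daily benzodiazepine, who must either stop a prescribed medicine or not use the study capsule. That patient must also recognise that the medicine counts as a centrally acting substance, and the second vial is labelled only as investigational medication.

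The plan treats its other named life-threatening risk differently. For NSAID bleeding, Risks/Benefits relies on patients having been screened for gastro-intestinal illness, and Exclusion criteria supplies that screen. The upper age limit is likewise justified by adverse drug effects. Eligibility is therefore the plan's usual tool for drug risk, but it is not used for this interaction. What is at stake is the safety of a small subgroup who could leave the ED with a seven-day blinded supply without anyone having been required to ask.

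**Working it through.** **Where a check could sit.** Each place in the protocol was read for a step that would identify a regular user of a non-analgesic sedative.

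- Exclusion criteria: daily or near-daily analgesics, anti-coagulants and alcoholism. A regular opioid user is caught as an analgesic user. A benzodiazepine, hypnotic or barbiturate user is not.
- Baseline measures: five questionnaires or ratings, with no medication item.
- Details of protocol: adds socio-demographics, back pain history and a urine pregnancy test. The off-protocol caution covers drugs taken for back pain, so it does not reach a sleeping tablet or an anxiolytic. The driving caution addresses drowsiness, not the interaction.
- Adverse events: side effects are assessed at the one-week call, when the seven-day supply is ending.

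**The plan's own figure.** Sample size calculation gives 50 per arm from a difference of 5, SD 8.9, alpha 0.05 (taken as two-sided) and power 0.80. The normal approximation is n = 2 × (1.960 + 0.842)² × 8.9² / 5² = 2 × 7.85 × 79.21 / 25 = 49.7, so 50. One route to the enrolment target is 50 / (1 − 1/3) / (1 − 0.05) = 78.9, consistent with 80 per arm. These figures stand, and nothing here changes them.

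**Allocation.** Randomization and blinding gives blocks of six with two orphenadrine, two methocarbamol and two placebo slots. The relaxant share is (2 + 2) / 6 = 2/3. With 3 × 80 = 240 enrolled, 240 × 2/3 = 160 are allocated to a relaxant.

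**Number of sedative users.** The documents give no prevalence. Let p be the proportion of otherwise eligible patients who regularly take a non-analgesic sedative, assumed to lie between 1% and 10%. Additional patients screened under the proposed exclusion = 240 / (1 − p) − 240.

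| Assumed p | Enrolled users, 240p | Allocated to a relaxant, 160p | Additional patients screened |
|---|---|---|---|
| 1% | 2.4 | 1.6 | 2.4 |
| 2% | 4.8 | 3.2 | 4.9 |
| 5% | 12 | 8 | 12.6 |
| 10% | 24 | 16 | 26.7 |

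The third column counts patients allocated to a relaxant. It does not count patients who take both drugs, and it supposes that physician referral removes none of them.

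**The case against.** The plan does not ignore the hazard. It discloses it, cautions every patient, excludes alcoholism and daily analgesic use, limits supply to seven days and has the capsule taken on demand when pain is at least moderate. An attending physician decides whom to refer. A safety committee meets monthly with the investigator to review adverse events and find ways to reduce them. The trial is meant to be widely generalisable, and Risks/Benefits reports relaxant use in 43% of ED visits for back pain. Managing interactions by advice and clinical judgement is a recognisable choice.

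Much of this stands, and it limits the point. Regular opioid users are already excluded, so the gap concerns non-analgesic sedatives only. The caution and on-demand dosing may well reduce co-exposure. A reader might apply the plan's remark that up to one third of earlier patients did not use the medication more than once, and infer that at least two thirds of sedative users allocated to a relaxant would take it repeatedly. The documents do not support that minimum, because any patient who heeds the caution lowers the count.

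A reader might also infer that nobody will ask about sedatives. Screening and case report forms are not in the documents, so the supportable statement is that the protocol text specifies no such step.

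The objection does not close the gap. Referral of appropriate patients names no sedative check. On-demand dosing protects only those who know their medicine is covered. The one-week call and the committee act after the supply has been handed over. In usual care the prescriber can withhold a relaxant from a particular patient. Here allocation is random and blinded, so the entry criteria have to do that work.

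**Conclusion.** The point holds as a cheap improvement for patient safety. Followed as written, the plan can randomise a regular user of a non-analgesic sedative with no safeguard specific to that drug beyond a general caution, against an interaction the plan itself regards as potentially lethal. Under an assumed prevalence of 1% to 10%, about 1.6 to 16 such patients would be allocated to a relaxant. The 2/3 share comes from the plan; the prevalence does not.

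A reader might take these figures as a count of co-exposed patients or of expected harms. They are neither: actual joint use is unknown, and the documents give no rate of harm. Nor does the point imply bias in the efficacy comparison, since randomisation distributes sedative users across the arms by chance. No figure in the protocol is wrong.

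**What to change.** Add one line to Exclusion criteria: *current daily or near-daily use of a prescribed non-analgesic sedative (benzodiazepine, hypnotic, barbiturate or other sedating muscle relaxant)*. The frequency threshold is the one the plan already applies to analgesics. Ask about it at the existing screening interview, which must already cover analgesics and anti-coagulants.

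Nobody should be asked to stop a prescribed drug in order to enter. Occasional users stay eligible and receive the existing caution with their own drug named. They are treated differently from regular users because they can reasonably leave out the occasional dose for a week. Drugs given in the ED before screening would not count and remain a matter for the attending physician.

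The cost is one exclusion line, one question and, under the same 1% to 10% assumption, about 3 to 27 additional otherwise eligible patients screened to enrol 240. The study population becomes slightly narrower, against the stated aim under Subject selection. The 80 per arm and the analysis are unchanged.
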